8.3 Source records

Source documents will be created and maintained by the investigational site team throughout the clinical study. The data reported on the PDA module will be derived from, and be consistent with, these source documents, and any discrepancies will be explained in writing.

8.4 Records retention

The CCISC PDA Module coordinator and Principal Investigators will maintain the clinical study documents as required. Measures will be taken to prevent accidental or premature destruction of these documents. The Principal Investigator or the CCISC may transfer custody of records to another person/party and document the transfer at the investigational site or the CCISC site, as appropriate. These documents must be retained by the investigational site for a period of 2 years after the conclusion of the clinical study and made available for monitoring or auditing by the CCISC or representatives of the applicable regulatory agencies. All original source documents must be stored for the maximum time required by the regulations at the hospital, research institute, or practice in question. If original source documents can no longer be maintained at the site, the investigator will notify the CCISC PDA Module PI.

9 Clinical Data Handling

The CCISC PDA Module will be responsible for the data handling. The CCISC and/or its affiliates will be responsible for compiling and submitting all required reports to governmental agencies. Data will be analyzed by the CCISC and maybe transferred to the any other worldwide regulatory authority in support of a market-approval application. CCISC will have the ability to send raw data and data analysis scrubbed of all PHI and institution information to industry, government agency or other worldwide regulatory authorities.

9.1 Protection of Personally Identifiable Information

The CCISC respects and protects personally identifiable information collected or maintained for this clinical study. The privacy of each subject and confidentiality of his/her information will be preserved in reports and when publishing any data. Confidentiality of data will be observed by all parties involved at all times throughout the clinical investigation. All data will be secured against unauthorized access.

9.2 Data Management Plan

A Data Management Plan (DMP) will describe procedures used for data review, database cleaning, and issuing and resolving data queries. If appropriate, the DMP may be updated throughout the clinical investigation duration. All revisions will be tracked and document controlled. Subject data will be captured in a validated electronic data capture (EDC) system hosted by the CCISC. Only authorized site personnel will be permitted to enter the CRF data through the EDC system deployed by CCISC. An electronic audit trail will be used to track any subsequent changes of the entered data.

9.3 Document and Data Control

9.3.1 Traceability of Documents and Data

The investigator will ensure accuracy, completeness legibility and timeliness of the data reported to the CCISC PDA Module on the CRFs and in all required reports.

9.3.2 Recording Data

The CRF will be reviewed by the authorized site personnel. An appropriate comment will be provided to explain changes to data reported on the CRF.

10 Monitoring

It is the responsibility of the CCISC PDA Module PI to ensure the clinical study is conducted, recorded and reported according to the approved CSP, subsequent amendment(s), applicable regulations and guidance documents. Monitoring will be conducted according to CCISC's Clinical Monitoring work instruction. Prior to beginning the clinical investigation, the CCISC will contact the

Investigator or designee to discuss the clinical study and data requirements. A designated monitor will periodically review the subject records and associated source documents. The investigator of each site shall make subject and clinical study records available to the clinical monitor. The percentage of data that the monitor decides to verify will be according to the discretion of the monitor. The CCISC will randomly audit ten percent of the patients entered in the PDA module from each institution. Service details are previously outlined in the applicable Service Agreement between the CCISC participating site and the CCISC.

11 Compliance Statement

11.1 Statement of Compliance

In addition to applicable regional or local laws and regulations, this clinical study will be conducted in compliance with the most current version of the World Medical Association (WMA) Declaration of Helsinki and 21 CFR Parts 50, 54, 56 and 812. In the event of any conflicts, local laws and regulations will have precedence and in such cases, good faith efforts will be made to adhere to the intent of the other documents. Each participating site will sign a Clinical Study Agreementby appropriate personnel and agree to be compliant with it. Sites will not start entering data on subjects undergoing PDA closures prior to obtaining IRB approval and relevant Regulatory Authority approval, if applicable, and authorization from the CCISC in writing for the clinical study. If additional requirements are imposed by the IRB or relevant Regulatory Authority, those requirements will be followed. If any action is taken by an IRB or a relevant Regulatory Authority with respect to the clinical study, that information will be forwarded to the CCISC.

11.2 Quality Assurance audits and Regulatory Inspections

The investigator and/or delegate should contact the CCISC immediately upon notification of a regulatory authority inspection at the site. A monitor or designee will assist the investigator and/or delegate in preparing for the audit. The CCISC may perform quality assurance audits, as required.

The Principal Investigator or institution will provide direct access to source data during and after the clinical investigation for monitoring, audits, IRB review and regulatory authority inspections, as required. The Principal Investigator or institution will obtain permission for direct access to source documents from the subject, hospital administration and national regulatory authorities before starting the clinical study.

11.3 Repeated and Serious Non-Compliance

In the event of repeated non-compliance or a one-time serious non-compliance, as determined by the CCISC, a monitor or designee will attempt to secure compliance by one or more of the following actions:

- a. Visiting the investigator,
- b. Contacting the investigator by telephone,
- c. Contacting the investigator in writing,

d. Retraining of the investigator.

If an investigator is found to be repeatedly non-compliant with the signed agreement, the CSP or any other conditions of the clinical investigation, the CCISC will either secure compliance or, at its sole discretion, terminate the investigator's participation in the clinical investigation. In case of termination, the CCISC will inform the responsible regulatory authority, as required, and ensure that the IRB is notified, either by the Principal Investigator or by the CCISC.

12 Suspension or premature termination of the clinical investigation

The CCISC reserves the right to terminate the clinical investigation at any stage, with appropriate written notice to the investigators, IRB and relevant regulatory authorities, if required.

A Principal Investigator, IRB or regulatory authority may suspend or prematurely terminate participation in a clinical study at the investigational sites for which they are responsible. The investigators will follow the requirements specified in the Clinical Study Agreement.

If suspicion of an unacceptable risk to subjects arises during the clinical study or when so instructed by the IRB or regulatoryauthority, the CCISC may suspend the clinical study while the risk is assessed. The CCISC will terminate the clinical study if an unacceptable risk is confirmed. If the CCISC completes an analysis of the reasons for the suspension, implements the necessary corrective actions, and decides to lift the temporary suspension, the CCISC will inform the Principal Investigators, IRB, or regulatory authority, where appropriate, of the rationale, providing them with the relevant data supporting this decision. Approval from the IRB or regulatory authority, where appropriate, will be obtained before the clinical study resumes. If the CCISC suspends or prematurely terminates the clinical study at an individual investigational site in the interest of safety, the CCISC will inform all other Principal Investigators.

13 Clinical Study Conclusion

Initial data collection will be limited to 500 subjects. Additional data collection beyond the initial cohort of 500 subjects may be done on a voluntary basis by participating sites/physicians. It is anticipated to take a minimum of three years to have the 500 Subjects needed for the conclusion of the study.

14 Publication Policy

Publications or presentations of clinical study methods or results will adhere to CCISC's publication policy, which is based on Good Publication Practices and International Committee of Medical Journal Editors (ICMJE) guidelines. A copy of the policy will be provided upon request of the investigator. Publication planning and authorship determinations will be overseen by the Publications Committee (see section 6.4.1), and investigators will be notified via email about the dissemination of study data and opportunities for involvement as authors on publications/presentations.

APPENDIX A: DEFINITIONS

NON-STUDY SPECIFIC DEFINITIONS

Adverse Event (AE)

Any untoward medical occurrence, unintended disease or injury or untoward clinical signs (including abnormal lab findings) in subjects, users, or other persons, whether or not related to the device under clinical investigation. This definition includes events related to the device as well as events related to the procedure.

Serious Adverse Event (SAE)

An adverse event that led to:

- a. Death
- b. A serious deterioration in the health of the subject that either resulted in:
 - i. A life threatening illness or injury
 - ii. A permanent impairment of body structure or function
 - iii. Prolonged hospitalization
 - iv. A medical or surgical intervention to prevent life threatening illness or injury
 - v. A malignant tumor
- c. Fetal distress, fetal death or a congenital abnormality or birth defect
- d. A planned hospitalization for a pre-existing condition or a procedure required by the CSP

Adverse Device Effect(ADE)

An adverse event related to the use of an investigational medical device. This definition includes adverse events resulting from insufficient or inadequate implantation, installation or operation, or any malfunction of the investigational medical device. This definition includes any event resulting from the use error or from intentional misuse of the investigational medical device.

Serious Adverse Device Effect (SADE)

Adverse device effect that has resulted in any of the consequences characteristic of a serious adverse event.

Unanticipated Adverse Device Effect (UADE)

As defined in 21 CFR§812.3, Unanticipated Adverse Device Effect (UADE) are defined as any serious adverse effect on health or safety or any life threatening problem or death caused by, or associated with a device, if that effect, problem, or death was not previously identified in nature, severity, or degree of incidence in the CSP or application (including supplementary plan or application), or any other unanticipated serious problem associated with a device that relates to the rights, safety, or welfare of subjects.

STUDYSPECIFIC DEFINITIONS

Related

The adverse event is related to the study device/procedure – i.e. an event that follows a reasonable temporal sequence from administration of the study intervention, follows a known or expected response pattern to the suspected intervention, that is confirmed by improvement on stopping and reappearance of the event on repeated exposure and that could not be reasonably explained by the known characteristics of the subject's clinical state.

In summary, the AE is related to any study device or procedure if the event satisfies all of following criteria:

- a. Has a reasonable temporal relationship to intervention (e.g. device implant)
- b. Could not readily have been produced or explained by the subject's clinical state or have been due to environmental or other interventions
- c. Follows a known pattern of response to intervention
- d. Disappears or decreases with reduction in dose or cessation of intervention and recurs with re-exposure

MajorComplication

Major complications are defined as device or procedure-related adverse events resulting in any of the following:

- a. Death
- b. Life-threatening adverse event,
- c. Persistent or significant disability/incapacity, and/or
- d. A major open surgical intervention which is performed by a surgeon under general anesthesia

Examples of Major Complications:

- a. Device or procedure related events leading to death
- b. Cardiac perforation requiring percutaneous (e.g., pericardiocentesis) or open surgical intervention
- c. Cardiac tamponade
- d. Embolization requiring open surgical procedure (e.g., open heart surgery or femoral vessel cut down procedure) to retrieve the device
- e. Persistent hemodynamic instability requiring emergency cardioversion/defibrillation therapy or emergency blood transfusion and/or institution of inotropic therapy
- f. Excessive blood loss or hemolysis requiring transfusion > 20 cc/kg
- g. Persistent or worsening respiratory instability
- h. Cerebral or pulmonary embolism
- i. Persistent cardiac arrhythmia requiring a pacemaker
- j. Arteriovenous fistula requiring open surgical intervention
- k. False aneurysm of the femoral artery requiring surgical intervention
- l. Femoral vessel thrombophlebitis treated with intravenous antibiotics
- m. Infection of the device (bacterial endocarditis)

Minor Complication

Minor complications are defined as device or procedure-related adverse events that do not fit the definition of a major complication. These will include adverse events which may require medical intervention but are not life threatening, are not likely to have long-term (> 6 months) sequelae, and do not require long term (> 6 months) therapy. The following are examples of adverse events considered to be minor complications:

- a. Embolization that occurs intra-operatively where the device is retrieved using a transcatheter approach (e.g., using a snare) without needing to perform an open surgical procedure, such as open heart surgery or an open femoral vessel cut down procedure.
- b. Reduced peripheral pulse (reversible) that can be managed with anti-thrombotic therapy (e.g., heparin, Aspirin)
- c. Cardiac perforation not requiring percutaneous (e.g., pericardiocentesis) or open surgical intervention
- d. Transient cardiac arrhythmia that is managed successfully with cardioversion or medication
- e. Hematoma of the groin not requiring open surgical intervention

PDA Residual Shunt Grades Definitions

Grade 0—none;

Grade 1—trivial (narrow jet adjacent to the device via the PDA). Note: the presence of flow via existing or newly formed aortopulmonary collaterals should not be considered as representing a shunt via the PDA. (see references in Appendix B by Skinner and Acherman)

Grade 2—mild (broader jet filling proximal left pulmonary artery branch and extending to main pulmonary artery);

Grade 3/4—moderate to severe (wide jet filling the main pulmonary artery and extending to pulmonary valve or distal pulmonary artery branches, which also may be accompanied with the presence of flow reversal in the abdominal aortic Doppler pattern during diastole)

Definitions of significant adjacent vessel stenosis (narrowing/obstruction)

1. Significant obstruction of the left pulmonary artery is defined as less than 30% flow to the left lung by lung perfusion scan or a peak instantaneous gradient in left pulmonary artery ≥35 mmHg by echocardiogram if lung perfusion scan is not available.OR

2. Significant obstruction of the aorta is defined as a gradient of $\geq 20 \text{ mmHg in the aortic}$ is thmus by invasive aortic catheterization or a mean gradient $\geq 20 \text{ mmHg in the aortic}$ is thmus by echocardiogram if invasive aortic catheterization is not available.

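### The relatedness test in Appendix A requires recurrence on re-exposure, which a one-time implant can hardly ever show; read literally, it empties the primary safety numerator

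*Protocol*

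**What the plan says.** Appendix A, under the study-specific definitions, states the relatedness rule twice. The narrative sentence describes a related event as one "that is confirmed by improvement on stopping and reappearance of the event on repeated exposure". The summary that follows reads "In summary, the AE is related to any study device or procedure if the event satisfies all of following criteria", and its criterion (d) is "Disappears or decreases with reduction in dose or cessation of intervention and recurs with re-exposure". Neither place says that the condition applies only where it can be observed.

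The two complication definitions build on this term: "Major complications are defined as device or procedure-related adverse events resulting in any of the following" and "Minor complications are defined as device or procedure-related adverse events that do not fit the definition of a major complication".

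Section 2.1 restricts the primary safety composite to major events related to the device or the procedure, in four categories: vascular access complications, valvular injury, device embolization, and pulmonary or aortic vessel stenosis. Section 7.1 speaks of major adverse events and refers to Appendix A for the definition. It plans an exact binomial 95% interval and a descriptive comparison with the IDE and Continued Access studies.

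**The concern.** Improvement on stopping and recurrence on re-exposure is a test suited to a drug that can be withdrawn and given again. Here the exposure is a single catheter procedure that leaves a permanent implant. There is no dose to reduce, the procedure is over when the event is assessed, and re-exposure would normally mean a second procedure.

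The relatedness term decides which events enter the primary safety numerator. A mandatory criterion that the intervention cannot satisfy therefore removes genuine complications from the count, while the denominator stays as it was. The study has no formal hypothesis (Section 7.6), so the estimated rate and its interval are the primary safety result. A rule that can only push that estimate down goes to the study's main purpose.

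**Working it through.** **1. Does the relatedness rule reach the endpoint?** Section 2.1 counts only device- or procedure-related major events. Section 7.1 omits the word related but sends the reader to Appendix A. The only matching definition there is Major Complication, which is itself limited to related events. The same limit applies to minor complications, so an event that fails the test is neither major nor minor.

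**2. Can the four endpoint categories meet criterion (d)?**
- Valvular injury: Section 2.1 describes damage with dysfunction after the procedure, so it is present once the intervention has ended. Recurrence would need another procedure.
- Access complications: recurrence would need repeat vascular access.
- Embolization and vessel stenosis: these could meet (d) only if the device were retrieved and re-deployed and the event then happened again. Section 2.1 and Appendix D do foresee retrieval and repositioning, so this is a real but narrow exception. The appendix classes intra-operative embolization with transcatheter retrieval as minor, so that form of the exception would not add to a count of major events.

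**3. Can the listed complications meet criterion (d)?** Death is the first outcome that makes a related event major, and a fatal event cannot recur. Tamponade, perforation and "Embolization requiring open surgical procedure" would ordinarily fail, because nothing is withdrawn and then repeated. "Persistent or worsening respiratory instability" and "Persistent cardiac arrhythmia requiring a pacemaker" are described by failing to resolve, which fits badly with a requirement to disappear or decrease. The rule and the examples it governs cannot both be applied as written.

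**4. Does another section supply a different standard?**
- Section 8.2 requires reporting of potentially related events and of events whose relatedness cannot be determined. It governs what is collected, not what is counted.
- Section 6.4.2 gives adjudication to the CEC and refers to adverse events as defined in Section 5. Section 5.1 points back to Appendix A.
- The serious adverse event form in Appendix G uses graded categories, including probable, possible, not related and not assessable. No rule maps them to the all-criteria definition.

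**5. Illustration of size.** The protocol gives no calculation to reproduce. Inputs:
- n = 500 (Section 2);
- a major complication rate of 4.0% to 10.0% (Section 7.1), a literature range for major complications overall and not an expected rate for this four-category composite;
- the share of true events that passes the rule, which is an assumption varied from all to none.

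Events before the rule: 500 × 0.04 = 20 and 500 × 0.10 = 50. The exact (Clopper-Pearson) limits for x events in n are the 2.5% quantile of Beta(x, n − x + 1) and the 97.5% quantile of Beta(x + 1, n − x). For x = 0 the lower limit is 0 and the upper limit is 1 − 0.025^(1/n).

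| Share of events passing | True rate 4% | True rate 10% |
|---|---|---|
| All | 20/500 = 4.0% (2.46 to 6.11) | 50/500 = 10.0% (7.51 to 12.97) |
| Half | 10/500 = 2.0% (0.96 to 3.65) | 25/500 = 5.0% (3.26 to 7.29) |
| A quarter | 5/500 = 1.0% (0.33 to 2.32) | 12/500 = 2.4% (1.25 to 4.15) |
| A tenth | 2/500 = 0.4% (0.05 to 1.44) | 5/500 = 1.0% (0.33 to 2.32) |
| None | 0/500 (0 to 0.74) | 0/500 (0 to 0.74) |

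A quarter of 50 is 12.5, entered as 12. For no events, 1 − 0.025^(1/500) = 0.74%. If a single event passed through the re-deployment exception, the result would be 1/500 = 0.2% (0.01 to 1.11). Section 7.4 will take the denominator below 500. With 400 analysed (an assumption), no events gives an upper limit of 1 − 0.025^(1/400) = 0.92%. At a true 4%, losing half the events already puts the upper limit (3.65%) below the true rate.

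**The case against.** The strongest reply is that nobody would apply the rule literally. The appendix names death, tamponade and device infection as major complications, Section 2.1 describes vessel stenosis in ordinary causal terms, and the CEC adjudicates under a charter that is not shown. A sensible adjudicator would treat (d) as inapplicable. This stands as a limit on the likely harm: what is proven is a contradiction in the text, not a bias in a reported result. It does not remove the defect, because an adjudicator who sets (d) aside departs from the written definition and the protocol offers no other.

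A second reply is that the list says if, not only if, so meeting all four criteria might be sufficient without being necessary. The list, however, summarises a definitional sentence containing the same requirement, and no other route to a related classification is given.

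Three further objections have force:
- The effect on the comparison with the IDE and Continued Access studies depends on how those studies defined relatedness, which the protocol does not say. No claim about comparability in either direction is made here.
- The re-deployment exception may be wider than intra-operative retrieval, since the adverse event form also records delayed embolization and occlusion with another device after retrieval. Even so, the event would have to happen again after re-deployment.
- Removing (d) does not settle everything. Criterion (b) remains demanding in infants with many co-morbidities, and the categories on the Appendix G form stay unmapped.

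The consequence is also softened because the events are reported on the wider threshold of Section 8.2 and can be reclassified.

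**Conclusion.** The point holds. The definition is wrong as written for a one-time implant, contradicts the complications listed in the same appendix, and governs the primary safety endpoint. Any effect on the rate is downward, because events leave the numerator while the denominator is unchanged.

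The size in practice is unknown. The limiting case of 0/500 (upper limit 0.74%), against 4.0% to 10.0% when all events count, rests on a literature rate borrowed from Section 7.1 and on no event meeting (d). It is not a forecast. The definition should be corrected, but the data are not at risk and no hypothesis test depends on the rate.

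**What to change.** In Appendix A, delete criterion (d) and the matching clause of the narrative sentence on improvement after stopping and reappearance on repeated exposure. Alternatively, limit both to situations where they apply. Keep criteria (a) to (c) as the standard for the safety endpoint and for major and minor complications, and check that the CEC charter uses the same standard. While the text is open, it would help to state which relationship categories on the Appendix G form count as related.

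The core change is two text edits and a charter check. It needs no new data, visits or subjects. The sponsor should expect that the reported safety rate may be less favourable than under the literal rule.
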